### 8.2. Exclusion Criteria

A subject who meets any of the following criteria will be excluded from this study:

1. CCI [REDACTED] screening ECHO or clinical signs and/or symptoms of cardiomyopathy.
2. Has had major surgery within 3 months prior to Day 1 or planned surgery or procedures that would interfere with the conduct of the study for any time during this study.
3. Has presence of any other clinically significant illness, including cardiac, pulmonary, hepatic, renal, hematologic, immunologic, or behavioral disease, or infection or

malignancy or concomitant illness or requirement for chronic drug treatment that in the opinion of the Investigator creates unnecessary risks for gene transfer or a medical condition or extenuating circumstance that, in the opinion of the Investigator, might compromise the subject's ability to comply with the protocol required testing or procedures or compromise the subject's wellbeing, safety, or clinical interpretability.

4. Has serological evidence of current, chronic, or active human immunodeficiency virus, hepatitis C, or hepatitis B infection.
5. Has a symptomatic infection (eg, upper respiratory tract infection, pneumonia, pyelonephritis, meningitis) within CCI prior to Day 1.
6. Demonstrates cognitive delay or impairment that could confound motor development in the opinion of the Investigator.
7. Has had treatment with any of the following therapies according to the time frames specified:
  - CCI
    - Gene therapy
    - Cell based therapy (eg, stem cell transplantation)
    - CRISPR/Cas9, or any other form of gene editing
  - CCI
    - Use of human growth factor or givinostat
  - CCI
    - Any investigational medication
    - Any treatment designed to increase dystrophin expression (eg, Translarna™, EXONDYS 51, VILTEPSO™)
8. Has received a live virus vaccine within CCI or inactive vaccine within CCI of the Day 1 visit or expects to receive a vaccination during the CCI after Day 1.
9. Has abnormal laboratory values considered clinically significant including but not limited to:
  - CCI
10. Has known hypersensitivity to delandistrogene moxeparvovec or any excipients of delandistrogene moxeparvovec.

11. Family does not want to disclose subject's study participation with general practitioner/primary care physician and other medical providers.
12. In the opinion of the Investigator, the subject is not likely to be compliant with the study protocol.

### **8.3. Screen Failures**

Screen failures are defined as subjects who consent to participate in the clinical study but are not subsequently randomly assigned to study drug. A minimal set of screen failure information including demography, screen failure details, eligibility criteria, and any SAE information are required to ensure transparent reporting of screen failure subjects. CCI [REDACTED]

Individuals who do not meet the criteria for participation in this study (screen failure) may be re-screened at the Investigator's discretion with Sponsor approval.

### **8.4. Completion of a Subject's Participation in the Study**

Subjects will be considered to have completed their participation in the study after they have completed the Part 2 Week 52/early termination visit or have withdrawn from the study.

### **8.5. Subject Withdrawal Criteria**

Any subject can decide to withdraw from study participation at any time for any reason. A subject who withdraws prior to dosing may be replaced at the discretion of the Sponsor. In addition, the Sponsor may decide to stop the study participation of any subject as deemed necessary. The Investigator may also stop the study participation of any subject at any time. Reasons for withdrawal from the study include, but are not limited to:

- The subject or parent(s)/legal guardian(s) withdraws consent.
- Prior to randomization and dosing it is determined that the subject was erroneously included in the study (ie, was found to not have met the eligibility criteria).
- The subject is unable to comply with the requirements of the protocol.
- The subject participates in another investigational study without prior written authorization of the Sponsor.

The Investigator or study staff will document the reason(s) for withdrawal on the electronic case report form (eCRF). If withdrawn subjects received study drug, every effort should be made to request that the subject allow follow-up for safety purposes.

Subjects who withdraw from the study must return the wearable device.

Subjects who have received study drug and withdraw from the study but do not withdraw consent will be asked to continue telephone calls to collect AEs and concomitant medications and have blood collected for laboratory assessments according to Section 2.3 CCI [REDACTED] after infusion (if subjects withdraw within this window), and then for

safety laboratory assessments approximately CCI starting from the date of the last safety laboratory assessment before withdrawal. For this study, safety laboratory assessments include the following: electrolytes, troponin, liver function, hematology, high-sensitivity C-reactive protein (hsCRP) and complement, renal function, and urinalysis (see Section 10.4.6.1 for a list of analytes associated with each parameter).

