| 
(delandistrogene moxeparovec or placebo). Refer to the study blinding plan for additional details. Starting the day prior to the infusion, all subjects will receive additional glucocorticoid (prednisone equivalent) for at least 60 days.
 

• A 104-week Follow-up Period (post Part 1 infusion) during which safety and efficacy parameters will be evaluated in Part 1 and Part 2. Subjects will be expected to attend both remote and in-person visits to complete required procedures/assessments. Additional unscheduled visits are allowed per the Investigator’s clinical judgement. For subjects who complete the study, the last study visit will occur at Part 2 Week 52. For subjects who prematurely discontinue post-infusion follow-up, an end of study/early termination visit will be required; however, each subject should be strongly encouraged to continue study follow-up until 52 weeks post each infusion.

 
Efficacy assessments will include the following:
 

• NSAA

• Time to rise from the floor

• 100MWR

• Time to ascend 4 steps

• 10MWR

• Real-world stride velocity, CCI [REDACTED] as assessed by a wearable device

• Muscle biopsy in a subset of subjects

• PROMIS in a subset of subjects

 
CCI [REDACTED]
 
CCI [REDACTED]
 
CCI [REDACTED]
 
CCI [REDACTED]
 
Safety assessments will include the following:
 

• Adverse events

• Vital signs

• Physical examination

• ECGs

• ECHOs

• Laboratory tests

 |   |

|  |   |
|--|---|
| NAME OF COMPANY:
Sarepta Therapeutics, Inc.
[name]
[name]
[contact]   | NAME OF FINISHED PRODUCT:
delandistrogene moxeparvec

NAME OF ACTIVE INGREDIENT:
delandistrogene moxeparvec |
| 
CCI [REDACTED]
 
CCI [REDACTED]
 
CCI [REDACTED]
 
After completion of the Part 2 Week 52 assessments, subjects will be eligible to enroll into an extension study to assess long-term safety and efficacy. All subjects will be followed for long-term safety and efficacy in the extension study for at least 5 years after delandistrogene moxeparvec infusion.
   |   |
| Number of Subjects (Planned): Approximately 120 subjects will be enrolled in this study.  |   |

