### **9.4. Treatment Compliance**

Delandistrogene moxeparvovec or placebo will be administered once by IV infusion under the direct supervision of trained study staff.

The study staff will maintain a record of the dispensing and administration of study drug for each subject via an accountability record or equivalent document.

Accurate recording of study drug administration will be made in the appropriate section of the subject's eCRF and source documents.

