#### **10.3.1.1. North Star Ambulatory Assessment**

The NSAA is a clinician-administered scale that rates performance on various functional activities (Mazzone 2010). It was designed to be used in boys with DMD who are able to stand, and it has been used in DMD boys of this study's age range ( $\geq 4$  and  $< 8$  years) (Connolly 2013, Mercuri 2016).

During this assessment, subjects perform 17 different functional activities, including the 10MWR, rising from a sit to a stand, standing on 1 leg, climbing a box step, descending a box step, rising from lying to sitting, rising from the floor, lifting head off floor, standing on heels, and jumping.

Subjects will be graded as follows: 2 = normal, no obvious modification of activity; 1 = modified method but achieves goal independent of physical assistance from another; and 0 = unable to achieve goal independently.

Details on administration of the NSAA are provided in the Clinical Evaluator Manual.

Two NSAA scores will be collected [CCI] at Baseline, [CCI] at Week 52 in Part 1, [CCI].

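### Section 8.5 lets an already infused boy be removed for non-compliance or unauthorized entry to another study and itself provides only safety follow-up, so his Part 1 Week 52 NSAA can be lost

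*Combined protocol and SAP*

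**What the plan says.** - **Discretion to remove (Section 8.5).** The section states that "the Sponsor may decide to stop the study participation of any subject as deemed necessary", and adds: "The Investigator may also stop the study participation of any subject at any time".
- **Listed reasons (Section 8.5).** They include "The subject is unable to comply with the requirements of the protocol" and "The subject participates in another investigational study without prior written authorization of the Sponsor". Only one listed reason carries a time limit: "Prior to randomization and dosing it is determined that the subject was erroneously included in the study".
- **After removal (Section 8.5).** Subjects who were infused and leave without withdrawing consent are asked for telephone calls on adverse events and medication and for laboratory samples. No functional assessment is named.
- **Aim of follow-up (Section 2.1, Methodology).** An early termination visit is required, and then: "each subject should be strongly encouraged to continue study follow-up until 52 weeks post each infusion". Section 8.5 does not repeat this.
- **Early termination (Section 7.1.3.1).** The visit is required, and the section names the NSAA; the timing is redacted.
- **Treatment (Sections 9.4, 7.1.2 and 9.3.1).** "Delandistrogene moxeparvovec or placebo will be administered once by IV infusion under the direct supervision of trained study staff". Part 2 then adds a blinded crossover infusion.
- **Analysis (Sections 12.3 and 12.4.4.1).** Efficacy is analysed in all randomized and treated boys, using a repeated-measures model that assumes data missing at random. Sensitivity analyses for departures from that assumption are planned.

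**The concern.** Stopping participation after Day 1 of Part 1 cannot undo or shorten the Part 1 infusion. What it mainly ends is the collection of outcomes up to Week 52, the primary time point. The two listed reasons and the open discretion leave that decision to the site or sponsor, even when the family has not withdrawn consent.

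The risk is missing data related to outcome. A boy who is declining may find the visits and motor tests hard, and a site could read this as inability to comply. If such boys are removed, the primary model predicts their Week 52 change from boys who stayed, and may predict it too favourably. The treatment comparison is biased only if this happens more in one arm: in favour of treatment if the treated arm loses more poor outcomes, and against it if the placebo arm does.

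**Working it through.** **Step 1. The texts side by side.** Section 8.5 restricts erroneous inclusion to the time before dosing and places no such limit on the other reasons, so they apply to infused boys. The synopsis wants follow-up to 52 weeks after each infusion. Section 8.5 offers a route out before then and arranges only safety contacts. Section 8.4 counts a withdrawn boy as having finished participation, and Section 12.5 lets the primary analysis proceed with boys who left Part 1 early. No visible text asks for a Week 52 NSAA from a boy whom the site or sponsor removed.

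**Step 2. The plan's own figure.** About 120 boys at 1:1 gives about 60 per arm. The effect, SD, power and dropout behind this are redacted, so it cannot be reproduced. Inverting the two-sample formula at two-sided 0.05:

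- Detectable effect = (1.960 + 0.842) × √(2/60) = 0.51 SD at 80% power
- Detectable effect = (1.960 + 1.282) × √(2/60) = 0.59 SD at 90% power

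With an assumed SD of 3.5 points these are 1.79 and 2.07 points.

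**Step 3. Simple arithmetic.** If k boys of 60 are lost from one arm and their true Week 52 change is d points worse than the model predicts, that arm's mean shifts by k × d / 60.

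- k = 1, d = 4: 4/60 = 0.07 points
- k = 3, d = 6: 18/60 = 0.30 points

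The difficulty is choosing a realistic d, so it was simulated.

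**Step 4. Simulation.** All inputs are assumptions: no true effect, 60 per arm, one earlier visit and Week 52, with correlation 0.5, 0.7 or 0.85 between the two. The k worst Week 52 values were removed from the treated arm only, with 6,000 runs per setting. The analysis was a likelihood-type estimate that keeps the earlier visit, as a stand-in for the planned model. Ranges run over the three correlations; the nominal rate of falsely favouring treatment is 0.025.

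| Lost from treated arm | Bias (SD) | False-favourable rate |
|---|---|---|
| 0 of 60 | about 0 | 0.025–0.026 |
| 1 of 60 | 0.01–0.03 | 0.031–0.036 |
| 3 of 60 | 0.03–0.08 | 0.041–0.071 |
| 6 of 60 | 0.06–0.15 | 0.058–0.148 |

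Using completers only, the loss of 3 gives a bias of about 0.10 SD and a rate of 0.088 to 0.092. The model therefore reduces the bias without removing it. With 3 lost from each arm (correlation 0.7) the bias is about 0. The rate is then 0.031, still slightly raised because trimming the worst values also shrinks the estimated variance.

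**Step 5. Scale.** The unadjusted standard error of the difference is √(2/60) = 0.183 SD. A bias of 0.03 to 0.08 SD is 0.16 to 0.44 standard errors, or about 0.1 to 0.3 points at the assumed SD of 3.5.

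**The case against.** Much of the plan softens the problem.

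- **Some data are kept.** An early termination visit is required, removed boys stay in the efficacy population, their earlier visits stay in the model, and sensitivity analyses for departures from missing at random are planned. This stands, but an NSAA at removal is not a Week 52 score, and a sensitivity analysis explores a gap without filling it.
- **The listed reasons do not order removal.** They are possible grounds, to be documented, and the synopsis urges continued follow-up. This is fair; the point is that the two sections pull in different directions and should be reconciled.
- **Blinding limits selection by arm.** This is largely right. It may be incomplete: evaluators are kept from GGT results (Section 9.3.2.4) while investigators must act on GGT rises (Section 9.5.1.2). That is an inference, not a documented event.

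Three stronger readings are tempting and are not supported.

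- A reader might infer that this is a one-infusion trial in which removal stops no treatment. Each boy is scheduled for a second infusion in Part 2, which for a Part 1 placebo boy is the active product, so removal forgoes that too. The crossover also gives a family that suspects placebo a reason to stay, and Section 8.5 concerns only unauthorized entry to another study.
- A reader might infer that the rule deletes the worst outcomes. No text ties either reason to poor function. The NSAA scores an undoable item as "0 = unable to achieve goal independently", so a boy who attends and scores zero has complied with testing.
- A reader might infer a half-point shift, from k = 3 and d = 10 (30/60 = 0.50). With an SD of 3.5 and correlation 0.7 the residual SD is 3.5 × √(1 − 0.49) = 2.5, so all three boys, in one arm, would lie 4 residual SDs below prediction. That is an extreme, not a planning case.

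**Conclusion.** The point holds in a limited form. Section 8.5 permits removal of an infused boy who has not withdrawn consent, arranges only safety contacts afterwards, and is at odds with the synopsis. The consequence is an avoidable loss of Week 52 NSAA scores. It produces bias only if removals relate to outcome and differ by arm, and then the bias is modest: about 0.03 to 0.08 SD with the three worst of 60 lost from one arm, and about 0 if losses balance.

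The number of removals, their selection and the visit correlation are assumptions, and the point values also assume the SD. The detailed SAP text and the Schedule of Events are not visible, so nothing is concluded about how these boys would be handled in the analysis. The change is still worth making because it is cheap and protects the primary endpoint.

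**What to change.** Reconcile Section 8.5 with the synopsis by separating the time before Part 1 dosing from the time after it. After Part 1 dosing:

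- Record non-compliance or entry to another study as a dated protocol deviation or intercurrent event. Neither by itself ends efficacy follow-up.
- Seek the Part 1 Week 52 NSAA from every infused boy unless consent is withdrawn.
- Have blinded staff document any other sponsor or investigator removal before Week 52, with its reason.

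Eligibility for Part 2 dosing in such boys is for the sponsor to settle, and NSAA scoring after a temporary injury belongs in the Clinical Evaluator Manual; neither is proposed here.

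The cost is revised wording and site training, using visits already scheduled. The downside is that a few boys with deviations remain in the data and must be handled as intercurrent events in the analysis.

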## **8.6. Subject Lost To Follow-up**

Every effort, as allowed by local and national law, will be made by the Investigator to contact the subject before the subject is declared lost to follow-up. These efforts may include but are not limited to the following:

- Attempt to contact the subject (or if applicable, the legal guardian who signed the informed consent on behalf of the subject) with at least 3 telephone calls to all telephone numbers for subject and other listed contacts (including in the evening and on weekends) and reschedule the missed visit as soon as possible and counsel the subject (or if applicable, the legal guardian who signed the informed consent on behalf of the subject) on the importance of maintaining the assigned visit schedule and ascertain whether or not the subject wishes to continue in the study.
- Call the primary care physician/general practitioner, referring specialist, and/or other listed physicians for more recent locator information, date of last office visit, or to determine mortality status.
- Send email and follow-up with mailing certified letters (return receipt requested) to all known subject addresses (or local equivalent methods) and all listed contacts (eg, relatives, friends, neighbors).
- Review subject's records and medical notes for any details of a hospitalization, doctor's visit, or other procedure that may indicate the status of the subject.
- Check local, regional, and national public records to locate subject or search for mortality status in accordance with local law.

All contact attempts should be documented in the subject's medical record. Once the site has exhausted and documented these actions, the subject will be considered to have withdrawn from the study.

## 9. STUDY TREATMENT

### 9.1. Description of Study Drug

Delandistrogene moxeparovec is supplied as a sterile, single use, frozen liquid for IV infusion. The frozen drug product must be thawed prior to the clinical administration. Refer to the study-specific Pharmacy Manual for further details.

#### 9.1.1. Package and Labeling

Please refer to the study-specific Pharmacy Manual for information on packaging and dosage preparation instructions.

#### 9.1.2. Study Drug Preparation

Please refer to the study-specific Pharmacy Manual for dosage preparation instructions.

#### 9.1.3. Storage

Delandistrogene moxeparovec must be stored at  $\leq -60^{\circ}\text{C}$ .

Study drug must be stored in an access controlled, locked room with appropriate temperature recording, controls, and monitoring.

Details for storage can be found in the study-specific Pharmacy Manual.

### 9.2. Study Treatment Administered

Subjects will be randomized in a 1:1 ratio by the IRT to one of the following treatment groups:

- Delandistrogene moxeparovec ( $1.33 \times 10^{14}$  vg/kg) by single IV infusion
- Placebo (saline, 0.9% sodium chloride solution) by single IV infusion

As required by the inclusion criterion, all subjects will be on a stable daily dose of oral corticosteroids for at least 12 weeks before the Screening visit, as detailed in Section 9.5.1. The day before the infusion (delandistrogene moxeparovec or placebo), the subject will be started on additional steroid for immunosuppression and will continue at this level for at least 60 days after the infusion (see Section 9.5.1.1). Following these 60 days, subjects may be tapered off of the added steroid and return to their baseline dose of corticosteroids for DMD and will remain on their stable dose (except for modifications to accommodate changes in weight) through the remainder of the study (see Section 9.5.1.2).

On Day 1, delandistrogene moxeparovec or placebo administration will be through a peripheral limb vein and performed according to the Administration Instructions (or Manual). CCI

XXXXXXXXXX A topical anesthetic cream (eg, lidocaine 2.5%, prilocaine 2.5%, LMX4 cream) may be applied to the skin prior to insertion of the IV catheter for infusions per site and subject preference. Prior to infusion, the IV catheter should be checked to confirm if it is within the vein and the IV flows well (is not interstitial).

### **9.3. Randomization and Blinding**

#### **9.3.1. Randomization**

Subjects will be randomized in a 1:1 ratio by the IRT to receive either delandistrogene moxeparovec ( $1.33 \times 10^{14}$  vg/kg) or placebo (saline, 0.9% sodium chloride solution) by single IV infusion. Subjects who received delandistrogene moxeparovec in Part 1 of the study will receive placebo in Part 2. Subjects who received placebo in Part 1 of the study will have the opportunity to receive delandistrogene moxeparovec in Part 2.

Randomization will be stratified CCI

#### **9.3.2. Blinding/Unblinding**

##### **9.3.2.1. Blinded and Unblinded Personnel**

All subjects, parents/caregivers, Investigators, and site staff with the exception of the unblinded site pharmacist will be blinded to the treatment the subject receives (delandistrogene moxeparovec or placebo). The unblinded pharmacist (or designee) will perform drug preparation according to the randomized treatment assigned. All documentation of study drug preparation will be maintained in a secure location which prevents access or disclosure to all blinded clinical study personnel. Refer to the study blinding plan for further details.

##### **9.3.2.2. Blinding for Muscle Biopsy Assessments**

Blinding for muscle biopsy assessments is outlined in the Biopsy Surgical and Laboratory Manual.

##### **9.3.2.3. Unblinding Procedures**

In the event of a medical emergency wherein the knowledge of the subject's treatment assignment may influence clinical decision-making, the Investigator has the option to unblind the subject's treatment assignment using the IRT system.

The blind of the treatment may be broken only in exceptional circumstances, such as when knowledge of the study treatment is essential for management of a subject's medical condition or AE. If time permits, the Investigator should contact the unblinded CRO Medical Director before unblinding the subject. If time does not permit, the Investigator may authorize breaking of the blind and then notify the unblinded CRO Medical Director. The study drug information should be disclosed only to personnel who need the information for the medical care of the subject. If the study treatment is unblinded, the subject number, time, date, and reason for unblinding must be recorded in the study records. Study personnel who were unblinded should be identified.

The reasons for any unblinding must be noted in the source documentation. The Investigator must not disclose information about treatment assignment to anyone aside from specific individuals who need the information because of their direct involvement in subject care.

Regulatory authorities and/or the IRB/IEC may request the unblinding of data from subjects at any time.

